## **Analytic Plan**

We will begin by examining the distribution and missingness of our outcome of interest, VAS. To take advantage of every available data point and account for repeated measures clustered within individual participants, we will run mixed-effect models in {STATA/SAS/R}, using a nested model-building process. If VAS is normally-distributed, we will specify linear mixed-effects models; otherwise, we may need to transform or dichotomize the outcome to ensure model assumptions are met. We will first run a simple model with only time (0, 6, 12, 18 weeks) as a Level I fixed effect predictor and VAS as a dependent variable, with the participant identification number included as a Level II random effect due to intra-individual correlation of VAS over time. Then, we will run increasingly complex models with intervention assignment (Cell Phone Support calls or texts n = 40 versus automated text reminders n = 20) included as a Level II fixed effect predictor, and then sex assigned at birth, focal medical diagnosis, medication complexity, age, and racial/ethnic identity as Level II fixed effect predictors, as well, to adjust for known or theoretical covariates. I will examine the impact of including increasing number of hypothesized predictors on model fit by examining AIC and  $R^2$ , and pare down the model if the model fit does not improve with all the hypothesized predictors included. This will lead to presenting parsimonious models that estimate the independent effect of the intervention on outcomes of interest, adjusted for all other predictors in the models. Finally, I will also assess whether model assumptions were met by plotting residuals versus fitted values. When I am

confident I have developed the most parsimonious, best-fitting model, I will calculate effect size estimates for the average difference in mean VAS between the Cell Phone Support call and text groups ( $n = 40$ ) and the automated text reminder group ( $n = 20$ ).

Then, we will follow the sample approach to predicting MEMS Caps adherence outcomes, and depression, social support, and self-efficacy. We will also run exploratory analyses using electronic-health record abstracted values (e.g., immunosuppressant levels, anti-epileptic drug levels, hemoglobin A1C, mean corpuscular volume/fetal hemoglobin) within focal diagnosis groups.

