Finally, for exploratory purposes, we will calculate pre-post effect sizes for subgroups of interest to explore whether interventions are comparably efficacious by focal diagnosis, gender, and racial/ethnic identity. Stratification was used to reduce the variation in potential confounders to be spread similarly between conditions, but that is not always entirely successful, especially in a small pilot trial. Therefore, we will conduct exploratory analyses including measured covariates as potential confounders or effect modifiers in the model-building process.

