### **Power Analysis**

Using STATA SE Version 15 software, we estimated the statistical power achieved with our proposed sample, assuming the Cohen's  $d$  effect size of 0.85 between groups seen in our preliminary data, within-subject intra-class correlation of 0.5 for repeated measures. We used the

design effect for clustered data (3 post-baseline measures, intraclass correlation=0.5) to compute the effective sample size for each group. The table below shows estimated power to detect differences in CPS (combined) versus automated reminders, and for the comparison of CPS strategies (original vs live text) in the total sample and by medical condition. To be more conservative, we also provide the statistical power for the CPS comparisons with a smaller effect size of 0.75 and 0.50. We also computed power to detect simple pre/post (e.g., baseline-12 week) changes between groups. There is approximately 87% statistical power for group comparisons using the combined sample with the effect size of 0.85; power is reduced for subgroup comparisons and the smaller effect size. However, as this study is a pilot randomized trial, the sample is more than sufficient to estimate effect sizes and assess feasibility for use in future proposals. See Table 1 for details.

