Cell Phone Support to Promote Medication Adherence Among Adolescents and Young Adults With Chronic Illness

NCT04241627

8/8/2022

This randomized pilot trial tested three different digital health interventions against one another (CPS-C, n = 11, CPS-T, n = 12, and ATR, n = 11). We are interested in the impact on self-reported medication adherence. We have 6 different measures of dependent variables (VAS1w, VAS2w, VAS3w, VAS1m, VAS2m, VAS3m). We assessed our dependent variables 4 occasions, at 0 weeks (pre-tx), 6 weeks (mid-tx), 12 weeks (post-tx), and 18 weeks (follow-up). We would like to run mixed-effect models to test for intervention effects of 1) both CPS conditions (CPS-C and CPS-T, n = 23) versus ATR (n = 11); and 2) the CPS conditions against each other, ignoring ATR (CPS-C, n = 11 versus CPS-T, n = 12). I also have covariates (sex assigned at birth, diagnosis, age) that we can include during nested model building procedures, and include in final reported models if they lead to best fit.

Can we begin by examining the distributions of our dependent variables, and discuss whether we should use linear mixed-effects models; otherwise, we may need to transform or dichotomize the outcome or use a different type of model (poisson? Negative binomial?) to ensure model assumptions are met?

Then, can we evaluate the impact of missing data on my results by re-running these analyses using inverse probably weighting. It is possible that missing data will not be completely at random (i.e., participants with lower medication adherence may also be less likely to adhere to the online survey schedule).

Finally, I would like to calculate effect sizes for subgroups (see the final table). See tables on the next pages.

Blank Tables

Table 5

Best-Fitting Models Predicting Self-Reported Adherence for Both CPS Conditions (C and T) versus ATR (N = 34)

Dependent Variables	VAS1w			VAS2w			VAS3w			VAS1m			VAS2m			VAS3m		
	Estimates	CI	p															
Fixed Effects																		
Intercept																		
Time																		
Intervention Group (both CPS versus ATR)																		
Random Effects																		
σ^2																		
τ_{00}																		
τ_{11}																		
ρ_{01}																		
ICC																		
N																		
Observations																		
Marginal R ² / Conditional R ²																		
AIC																		

Note—Make ATR the reference group so the estimate tells us how the combined CPS groups compare

Table 6

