Best-Fitting Models Predicting Self-Reported Adherence for CPS-T versus CPS-C (N = 23)

Dependent Variables	VAS1w			VAS2w			VAS3w			VAS1m			VAS2m			VAS3m		
	Estimates	CI	p															
Fixed Effects																		
Intercept																		
Time																		
Intervention Group (CPS-T versus CPS-C)																		
Random Effects																		
σ^2																		
τ_{00}																		
τ_{11}																		
ρ_{01}																		
ICC																		
N																		
Observations																		
Marginal R ² / Conditional R ²																		
AIC																		

Note—Make CPS-C the reference group so the estimate tells us how CPS-T compares

Table 7

Exploratory Analyses Estimating Effect Sizes Using Self-Reported Outcomes Past Week (Pre-Post... Baseline to 12 weeks)

Subgroup	n	d	CI	p	Subgroup	n	d	CI	p
VAS1w									
Total Sample	--	--	--	--	Young Men	--	--	--	--
CPS Combined vs. ATR	34				CPS Combined vs. ATR				
CPS-T vs. CPS-C					CPS-T vs. CPS-C				
Sickle Cell Disease	--	--	--	--	Young Women	--	--	--	--
CPS Combined vs. ATR	14				CPS Combined vs. ATR				
CPS-T vs. CPS-C					CPS-T vs. CPS-C				
Solid Organ Transplant	--	--	--	--	Latinx	--	--	--	--
CPS Combined vs. ATR	10				CPS Combined vs. ATR				
CPS-T vs. CPS-C					CPS-T vs. CPS-C				
Type 2 Diabetes	--	--	--	--	Black	--	--	--	--
CPS Combined vs. ATR	10				CPS Combined vs. ATR				
CPS-T vs. CPS-C					CPS-T vs. CPS-C				
VAS2w									
Total Sample (N = 34)	--	--	--	--	Young Men	--	--	--	--
CPS Combined vs. ATR					CPS Combined vs. ATR				
CPS-T vs. CPS-C					CPS-T vs. CPS-C				
Sickle Cell Disease (n = 14)	--	--	--	--	Young Women	--	--	--	--
CPS Combined vs. ATR					CPS Combined vs. ATR				
CPS-T vs. CPS-C					CPS-T vs. CPS-C				
Solid Organ Transplant (n = 10)	--	--	--	--	Latinx	--	--	--	--
CPS Combined vs. ATR					CPS Combined vs. ATR				
CPS-T vs. CPS-C					CPS-T vs. CPS-C				
Type 2 Diabetes (n = 10)	--	--	--	--	Black	--	--	--	--
CPS Combined vs. ATR					CPS Combined vs. ATR				
CPS-T vs. CPS-C					CPS-T vs. CPS-C				
VAS3w									
Total Sample (N = 34)	--	--	--	--	Young Men	--	--	--	--
CPS Combined vs. ATR					CPS Combined vs. ATR				
CPS-T vs. CPS-C					CPS-T vs. CPS-C				
Sickle Cell Disease (n = 14)	--	--	--	--	Young Women	--	--	--	--
CPS Combined vs. ATR					CPS Combined vs. ATR				
CPS-T vs. CPS-C					CPS-T vs. CPS-C				

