Solid Organ Transplant (n = 10)	--	--	--	--	Latinx	--	--	--	--
CPS Combined vs. ATR					CPS Combined vs. ATR				
CPS-T vs. CPS-C					CPS-T vs. CPS-C				
Type 2 Diabetes (n = 10)	--	--	--	--	Black	--	--	--	--
CPS Combined vs. ATR					CPS Combined vs. ATR				
CPS-T vs. CPS-C					CPS-T vs. CPS-C				

Table 8

Exploratory Analyses Estimating Effect Sizes Using Self-Reported Outcomes Past Month

Subgroup	n	d	CI	p	Subgroup	n	d	CI	p
VAS1m									
Total Sample	--	--	--	--	Young Men	--	--	--	--
CPS Combined vs. ATR					CPS Combined vs. ATR				
CPS-T vs. CPS-C					CPS-T vs. CPS-C				
Sickle Cell Disease	--	--	--	--	Young Women	--	--	--	--
CPS Combined vs. ATR					CPS Combined vs. ATR				
CPS-T vs. CPS-C					CPS-T vs. CPS-C				
Solid Organ Transplant	--	--	--	--	Latinx	--	--	--	--
CPS Combined vs. ATR					CPS Combined vs. ATR				
CPS-T vs. CPS-C					CPS-T vs. CPS-C				
Type 2 Diabetes	--	--	--	--	Black	--	--	--	--
CPS Combined vs. ATR					CPS Combined vs. ATR				
CPS-T vs. CPS-C					CPS-T vs. CPS-C				
VAS2m									
Total Sample	--	--	--	--	Young Men	--	--	--	--
CPS Combined vs. ATR					CPS Combined vs. ATR				
CPS-T vs. CPS-C					CPS-T vs. CPS-C				
Sickle Cell Disease	--	--	--	--	Young Women	--	--	--	--
CPS Combined vs. ATR					CPS Combined vs. ATR				
CPS-T vs. CPS-C					CPS-T vs. CPS-C				
Solid Organ Transplant	--	--	--	--	Latinx	--	--	--	--
CPS Combined vs. ATR					CPS Combined vs. ATR				
CPS-T vs. CPS-C					CPS-T vs. CPS-C				
Type 2 Diabetes	--	--	--	--	Black	--	--	--	--
CPS Combined vs. ATR					CPS Combined vs. ATR				
CPS-T vs. CPS-C					CPS-T vs. CPS-C				
VAS3m									
Total Sample (N = 34)	--	--	--	--	Young Men	--	--	--	--
CPS Combined vs. ATR					CPS Combined vs. ATR				
CPS-T vs. CPS-C					CPS-T vs. CPS-C				
Sickle Cell Disease (n = 14)	--	--	--	--	Young Women	--	--	--	--
CPS Combined vs. ATR					CPS Combined vs. ATR				
CPS-T vs. CPS-C					CPS-T vs. CPS-C				
Solid Organ Transplant (n = 10)	--	--	--	--	Latinx	--	--	--	--
CPS Combined vs. ATR					CPS Combined vs. ATR				
CPS-T vs. CPS-C					CPS-T vs. CPS-C				
Type 2 Diabetes (n = 10)	--	--	--	--	Black	--	--	--	--
CPS Combined vs. ATR					CPS Combined vs. ATR				
CPS-T vs. CPS-C					CPS-T vs. CPS-C

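### Tables 7 and 8 plan subgroup effect sizes d without a stated small-sample correction or standardising SD; the usual d would run about 7% to 19% high on average in the diagnosis rows

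*SAP*

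**What the plan says.** The SAP's opening text asks for the analysis in one sentence: "Finally, I would like to calculate effect sizes for subgroups (see the final table"). It gives no estimator, no standardising SD and no small-sample correction. The shells that follow are Table 7, "Exploratory Analyses Estimating Effect Sizes Using Self-Reported Outcomes Past Week", whose title goes on to give a pre-post window from baseline to week 12, and Table 8, "Exploratory Analyses Estimating Effect Sizes Using Self-Reported Outcomes Past Month". Both have columns n, d, CI and p. Each row block carries two contrasts: both CPS arms against ATR, and CPS-T against CPS-C.

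The diagnosis subgroups are given as 14 (sickle cell disease), 10 (solid organ transplant) and 10 (type 2 diabetes). The n for the CPS-T against CPS-C rows and for the gender and racial/ethnic rows is blank. The arm sizes are "CPS-C, n = 11, CPS-T, n = 12, and ATR, n = 11".

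In the protocol, Analytic Plan says that "for exploratory purposes, we will calculate pre-post effect sizes for subgroups of interest", to see whether the interventions work comparably by diagnosis, gender and racial/ethnic identity. Cohen's d is named only in Power Analysis, and it is the only standardised effect size that either document names.

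**The concern.** Cohen's d with a pooled SD is biased away from zero in small samples, because the SD in the denominator is itself estimated from few people. The bias depends on the degrees of freedom, so it differs from row to row of the same table. The purpose of Tables 7 and 8 is to compare effects across subgroups. For the same non-zero true effect, a smaller subgroup has a larger expected d, and nothing in the table shows the reader that part of the difference comes from the estimator. A simple multiplier removes nearly all of this bias and also lowers the variance of the estimate.

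**Working it through.** The documents give no figure for the bias of d, so there is none to reproduce. The 87% in Power Analysis concerns the power of a test and does not enter here.

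**Row sizes.** The total-sample rows have n = 34 (CPS against ATR, 23 v 11) and n = 11 + 12 = 23 (CPS-T against CPS-C). The diagnosis groups sum to 14 + 10 + 10 = 34, the whole sample. The three CPS-T against CPS-C diagnosis rows must therefore sum to 23. Since 23/3 = 7.67, at least one has n of 7 or fewer, however the arms fell within diagnosis.

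**Bias.** Assume d = difference in means / within-subgroup pooled SD, with df = n − 2. Then E[d] = δ/J, where δ is the true effect and J = Γ(df/2) / [√(df/2) Γ((df − 1)/2)], which is approximately 1 − 3/(4df − 1). For example, df = 8 gives 1 − 3/31 = 0.903.

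| n | df | 1 − 3/(4df − 1) | exact J | average overstatement, 1/J − 1 | E[d] if δ = 0.50 | E[d] if δ = 0.85 |
|---|---|---|---|---|---|---|
| 34 | 32 | 0.976 | 0.976 | 2.4% | 0.51 | 0.87 |
| 23 | 21 | 0.964 | 0.964 | 3.8% | 0.52 | 0.88 |
| 14 | 12 | 0.936 | 0.936 | 6.8% | 0.53 | 0.91 |
| 10 | 8 | 0.903 | 0.903 | 10.8% | 0.55 | 0.94 |
| 7 | 5 | 0.842 | 0.841 | 18.9% | 0.59 | 1.01 |

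The value 0.85 is the protocol's planning effect; 0.50 is the smallest effect size mentioned in Power Analysis.

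**Bias against sampling error.** Approximate SE(d) = √[(n1 + n2)/(n1·n2) + d²/(2(n1 + n2))]. The splits within diagnosis are not in the documents. I assume 9 v 5, 7 v 3 and 4 v 3, close to what 1:1:1 allocation would give. At d = 0.5 the 95% CI half-width (1.96 × SE) is:

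- n = 14: 1.11, against a bias of 0.03
- n = 10: 1.37, against a bias of 0.05
- n = 7: 1.52, against a bias of 0.09
- n = 34 (23 v 11): 0.73, against a bias of 0.01

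**Dependence on the SD.** If d were standardised by a total-sample SD (df about 32), the bias in every subgroup row would be about 2%, and correcting with the subgroup's own df would over-correct.

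**If a later trial were sized on one row.** With a true effect of 0.50, two-sided 5% and 80% power, n per arm = 2(1.96 + 0.842)²/0.50², rounded up to 63. Sized on the expected d of an n = 10 row (0.554), the plan would be 52 per arm, with true power 0.72. Sized on the N = 34 row (0.512), it would be 60 per arm, with power 0.78.

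**The case against.** The strongest reply is that nothing shows the correction will be left out. The tables are blank shells, d is undefined, and many analysts report a corrected value under that letter. This stands in part: that d is uncorrected is inferred from silence. But Cohen's d is the only such measure named, and if a correction is intended the SAP still needs the line that says so.

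The second reply is that the subgroup values are labelled exploratory and sampling error swamps the bias. Both statements are true, and they keep the point minor. They do not remove it: the planned CI shows the imprecision, whereas the bias is not visible to the reader.

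Three stronger readings are tempting, and the documents do not support them.

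- A reader might infer that the smallest subgroups will look the most responsive. The bias multiplies magnitude. It is zero if the true effect is zero, it makes a negative effect more negative, and it holds only on average. Between n = 14 and n = 10 the expected difference is 0.02 at a true effect of 0.50, so chance will decide which subgroup looks best.
- A reader might infer that these subgroup values are what the pilot exists to pass on. The protocol's statement that "the sample is more than sufficient to estimate effect sizes and assess feasibility for use in future proposals" concerns the sample as a whole. Its main planned effect size compares the combined CPS arms with ATR: "I will calculate effect size estimates for the average difference in mean VAS between the Cell Phone Support call and text groups" on one side and the reminder group on the other. The total-sample rows carry a bias of only 2% to 4%.
- A reader might infer that the next trial will be underpowered at about 72%. That follows only if it is sized on an n = 10 row, which neither document proposes.

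**Conclusion.** The point holds as a minor improvement to reporting. On the usual definition of d, the planned values overstate a non-zero effect on average by about 7% (n = 14), 11% (n = 10) and 19% (n = 7), against 2.4% and 3.8% in the total-sample rows. The consequence is a slight distortion of the exploratory comparison across subgroups.

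This rests on two assumptions: that no correction is applied, and that the SD is the pooled SD within each subgroup. The sizes 14 and 10 are printed in the SAP, and 7 or fewer in at least one row follows from its totals. Any smaller figure for a particular row would be a guess, although missing 12-week surveys would shrink the cells and raise the bias. The gap that comes first is the undefined SD, because the right correction cannot be chosen until it is fixed.

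**What to change.** 1. In the SAP, define d for the baseline-to-12-week comparison: the numerator, and which SD standardises it (baseline, change score, within-subgroup pooled, total-sample or model-based). Say whether the same definition holds in Table 8, whose title gives no time window.
2. In Tables 7 and 8 report Hedges' g = d × (1 − 3/(4df − 1)), with its CI, using the df that belongs to the chosen SD. At these sizes a noncentral-t or bootstrap interval is preferable.
3. State in the table notes that the correction was applied and with which SD. It would help to add that subgroup rows will not be used to size a future trial.

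The cost is a few lines of SAP wording and one line of code, with no new data. The downside is slightly smaller reported effect sizes. The correction does not cure the imprecision of rows with 14 or fewer people, and the text should say so.

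### Table 7's between-arm d reads as an unadjusted change score (Table 8's only by analogy); a week 12 difference adjusted for week 0 VAS would make the exploratory total-sample rows more precise

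*SAP*

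**What the plan says.** The SAP's Table 7 shell has columns for n, d, CI and p. Its rows are CPS combined against ATR and CPS-T against CPS-C, for the total sample and for subgroups by diagnosis, sex and ethnicity. Its heading ends "Using Self-Reported Outcomes Past Week (Pre-Post... Baseline to 12 weeks)". Table 8 has the same layout for the past-month items, but its heading is only "Exploratory Analyses Estimating Effect Sizes Using Self-Reported Outcomes Past Month", with neither a pre-post label nor a visit.

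The protocol's Analytic Plan describes the same exercise: "for exploratory purposes, we will calculate pre-post effect sizes for subgroups of interest". Its Power Analysis adds: "We also computed power to detect simple pre/post (e.g., baseline-12 week) changes between groups".

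No formula for d and no standardising SD is given. The covariates listed in the SAP are sex, diagnosis and age. The protocol adds medication complexity and racial/ethnic identity. Week 0 VAS is in neither list. The n column is partly pre-filled with 34, 14, 10 and 10, that is, everyone in the SAP, and these tables have no rule for a missing week 12 survey.

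**The concern.** If d is the difference between arms in raw week 0 to week 12 change, the analysis fixes the slope of week 12 on week 0 at 1. When the two visits correlate well below 1, that over-corrects. An arm that starts higher by chance has its change pulled down by more than regression to the mean warrants, and the interval is wider than the same data allow. Randomisation was stratified by sex and diagnosis, not by VAS, and with 23 v 11 participants chance gaps in week 0 VAS will not be small.

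What is at stake is the precision of the pilot effect sizes. The Power Analysis gives estimating effect sizes for future proposals as a purpose of the sample. Table 7's total-sample rows are the only treatment contrasts in the SAP shells that are explicitly tied to week 12; Tables 5 and 6 have time and group rows but no group-by-time row.

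**Working it through.** **The plan's own figure.** The Power Analysis assumes an "effect size of 0.85 between groups seen in our preliminary data, within-subject intra-class correlation of 0.5 for repeated measures" and reports about 87% power. Two-sided 5% is assumed here, as alpha is not stated. With 40 v 20 and one measure per person, 0.85 × √(40×20/60) = 3.10, and 3.10 − 1.96 = 1.14, so power is 87.4%. A raw-change comparison at r = 0.5 gives the same value, because 2(1 − 0.5) = 1. The match therefore cannot show which analysis was meant. (The described route, a "design effect for clustered data (3 post-baseline measures, intraclass correlation=0.5)", gives a design effect of 1 + 2×0.5 = 2, an effective 60 v 30 and 96.7%. That is a separate matter.)

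**Inputs.** Arm sizes of 23 v 11 and 12 v 11, and subgroup totals of 14, 10 and 10, come from the SAP. The documents give no week 0 to week 12 correlation r. The stated 0.5 is an intra-class correlation that the protocol applies to the three post-baseline measures, so r = 0.3 to 0.7 is used as an assumed range. Arm splits within subgroups are assumed. k is the week 12 SD divided by the week 0 SD, and is not given.

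**Formulas, in week 0 SD units.**
- Variance per person, raw change: 1 + k² − 2rk, which is 2(1 − r) when k = 1.
- Variance per person, adjusted for week 0: k²(1 − r²).
- The difference between them is (1 − rk)². Raw change carries −(1 − rk) times the chance week 0 gap, which is −(1 − r) when k = 1.
- 95% half-width: t × √variance × √(1/n1 + 1/n2), on n − 2 df for change and n − 3 for adjusted. The adjusted variance is multiplied by 1 + 1/(n − 4), with n = n1 + n2.

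**Worked case, 23 v 11, r = 0.5, k = 1.** √(1/23 + 1/11) = 0.367. Change: 2.037 × 1 × 0.367 = 0.75. Adjusted: 2.040 × 0.866 × 0.367 × 1.016 = 0.66. Change is 13% wider.

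| Comparison | r = 0.3 | r = 0.5 | r = 0.7 |
|---|---|---|---|
| 23 v 11: change / adjusted width | 1.22 | 1.13 | 1.07 |
| 12 v 11 | 1.21 | 1.12 | 1.05 |
| 9 v 5 (assumed split of 14) | 1.17 | 1.09 | 1.02 |
| 7 v 3 (assumed split of 10) | 1.12 | 1.04 | 0.98 |
| 4 v 3 (assumed CPS-T v CPS-C) | 0.99 | 0.93 | 0.87 |

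All rows have k = 1 and a separate fit in each group. Simulations at r = 0.5 and 0.7 agree to within about 0.03.

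**Chance imbalance.** The week 0 gap at 23 v 11 has SD 0.37, so a one-SD gap moves the raw-change difference by 0.5 × 0.37 = 0.18 SD at r = 0.5 (0.26 at r = 0.3, 0.11 at r = 0.7). Simulated slopes of the estimate on the gap at r = 0.5 were −0.49 for change and 0.00 for adjusted.

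**Unequal SDs, 23 v 11.** At r = 0.5 the ratio is 1.36 for k = 0.75, 1.13 for k = 1, 1.04 for k = 1.25 and 1.00 for k = 1.5. At k = 1.25 it is 1.11 for r = 0.3 and 0.99 for r = 0.7.

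**Common slope in a subgroup.** This was simulated with subgroups split 9 v 5, 7 v 3 and 7 v 3, r = 0.5 and k = 1. The mean half-width in a 7 v 3 subgroup is 1.54 for raw change, 1.46 for a separate adjusted fit, and 1.23 with one slope and one residual variance from all 34. Pooling the variance alone brings raw change to 1.40, so the slope accounts for a 12% narrowing (1.23 against 1.40).

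**The case against.** The best case for leaving the tables alone has four parts.

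- **Raw change is inferred.** No formula is given, and the Power Analysis sentence concerns a power calculation, not these tables. This stands as a limit on the claim. It does not rescue the text, because a d without contrast or standardiser still has to be defined.
- **Equal SDs are doubtful.** Entry required agreed adherence below 80% and VAS is bounded at 0 and 100, so the spread may differ at week 12. This stands. It can shrink the gain to nothing or enlarge it.
- **Most rows are subgroups**, where separate adjusted fits gain little or lose. This stands. A common slope recovers a gain, but assumes one slope across diagnoses, sexes and ethnic groups, which 34 people can barely check.
- **The tables are exploratory**, and the protocol already derives an overall CPS v ATR effect size from its final mixed model. This stands and limits the consequence.

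Three stronger readings are tempting and are not supported. A reader might infer that the change score itself excludes people without a week 12 survey, against the protocol's aim "To take advantage of every available data point and account for repeated measures clustered within individual participants". An adjusted analysis of week 12 alone uses the same complete cases, and that sentence concerns the mixed models. A reader might count wide intervals and baseline imbalance as two harms, or call d biased. With complete data and randomisation the change score is unbiased, and (1 − rk)² shows that the imbalance is the excess variance. A reader might also extend the point to Tables 5 and 6, which are separate models.

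**Conclusion.** The point holds for the total-sample rows of Table 7 on the most natural reading of the heading. For Table 8 it holds only by analogy and through the protocol's general wording. At 23 v 11, raw change gives intervals about 6% to 22% wider than baseline adjustment (5% to 21% at 12 v 11), for r from 0.7 to 0.3 with equal SDs. At r = 0.5 the excess falls to about 4% if the week 12 SD is 1.25 times baseline, and to none at 1.5 times. No general gain can be claimed for subgroups of ten or fewer fitted separately. No size can be put on the effect of missing week 12 surveys, since neither document gives a loss rate. This is a clarification worth making, with consequences confined to exploratory effect sizes.

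**What to change.** 1. In Tables 7 and 8, define d as the week 12 between-arm difference adjusted for week 0 VAS, divided by a stated SD, for example the pooled week 0 SD.
2. Take the total-sample rows from a longitudinal model using all available visits, so that people without a week 12 survey still contribute. With week 0 as a covariate, this keeps anyone who has a week 6 or week 18 survey. With week 0 as an outcome and arm means constrained equal there, it keeps everyone with any survey. A model of week 12 alone would not achieve this.
3. For subgroups, use a baseline slope estimated on the whole sample and state that a common slope is assumed. For CPS-T against CPS-C, say whether ATR data inform that slope, because the SAP sets ATR aside for this comparison.
4. Put the time point in Table 8's heading, and replace the pre-filled n by the number contributing at week 12.

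The cost is SAP wording and some code, with no new data. The statistical price is one degree of freedom and the common-slope assumption. The subgroup contrasts need more programming than the total-sample rows.
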